1 PROTOCOL SUMMARY

1.1 Synopsis

Protocol Title: A Phase 2, Multicenter, Open-label Study to Evaluate the Pharmacokinetics and Safety of RLYB212 in Pregnant Women at Higher Risk for HPA-1a Alloimmunization

Short Title: Phase 2 Study on the Pharmacokinetics and Safety of RLYB212 in Pregnant Women at Higher Risk for HPA-1a Alloimmunization

Rationale: RLYB212 is a human monoclonal anti-human platelet antigen (HPA)-1a immunoglobulin G antibody designed to selectively bind to HPA-1a positive fetal derived cells or cell fragments present in the maternal circulation. The therapeutic goal of RLYB212 is to drive the rapid and complete elimination of HPA-1a positive fetal antigen from the maternal circulation in HPA-1b/b pregnant women and prevent maternal HPA-1a alloimmunization.

A prophylactic dose regimen consisting of a single 0.12 mg subcutaneous (SC) loading dose of RLYB212 no later than gestational week (GW) 16 followed by 0.06 mg SC every 4 weeks (Q4W) through parturition is proposed for HPA-1b/b pregnant women at risk for HPA-1a alloimmunization. This dose regimen is the result of exposure simulations in pregnant women using a clinical pharmacology model based on pharmacokinetic (PK) and pharmacodynamic (PD) single and multiple dose data from two clinical studies with RLYB212 in HPA-1b/b volunteers, a meta-analysis of monoclonal antibody PK parameters, allometric scaling to account for demographic differences between study populations (Phase 1/non-pregnant and pregnant), and the dynamic physiologic changes that occur during gestation. The dose regimen is intended to achieve near steady state RLYB212 concentrations after the first dose and for steady state concentrations to be maintained within a target range of ~3 ng/mL to ~10 ng/mL for the duration of the pregnancy.

The target lower boundary is supported by clinical and preclinical data demonstrating that concentrations of RLYB212 sufficient to bind ~10% of HPA-1a positive receptors in an antigen challenge model are effective to drive rapid elimination of circulating HPA-1a positive antigen positive cells. The target upper boundary of ~10 ng/mL is supported by a comprehensive toxicology program that demonstrated RLYB212 to have no observed adverse effect level (NOAEL) margins of up to 242-fold greater than 10 ng/mL in antigen negative dams bearing heterozygous antigen positive offspring (representative of HPA-1b/b women bearing an HPA-1a positive fetus and at risk of alloimmunization) and projected exposures well over 10-fold greater than 10 ng/mL in antigen positive fetuses and neonates (representative of HPA-1a/b fetuses and neonates). The target upper boundary is further informed by an extensive review of available literature on clinical assessments of HPA-1a alloimmunization and fetal and neonatal alloimmune thrombocytopenia (FNAIT), where a maternal HPA-1a alloantibody level of 3 IU/mL has been reported as the threshold for the occurrence of anti-HPA-1a antibody-mediated fetal/neonatal thrombocytopenia. Using the most conservative estimates for binding equivalence in IU for RLYB212, the steady state upper boundary exposure target accounts for an additional margin of safety by maintaining RLYB212 concentrations at or below ~0.5 IU/mL.

The purpose of this Phase 2 study is to assess the PK and safety of RLYB212 at the proposed therapeutic dose regimen in HPA-1b/b pregnant women at higher risk for HPA-1a alloimmunization and FNAIT. Following confirmation of the prophylactic RLYB212 dose regimen, it is planned to evaluate the safety and efficacy of RLYB212 in a Phase 3 registration trial in pregnant women at higher risk for the occurrence of HPA-1a alloimmunization and FNAIT.

Objectives and Endpoints (Interventional/Study IPA2202)

Objective	Endpoint
Primary	

To evaluate the PK profile of RLYB212 during pregnancy following repeat SC administration	
Maternal PK parameters, eg,
half-life of RLYB212 ($t_{1/2}$)maximum RLYB212 concentration (C_{max})time to maximum RLYB212 concentration (t_{max})apparent clearance (CL/F) of RLYB212apparent volume of distribution (Vd)area under the RLYB212 concentration versus time curve (AUC)

To assess maternal and fetal safety of RLYB212 during pregnancy	
Type, seriousness, and incidence of AEsPhysical examination findingsVital signsMaternal clinical laboratory valuesECGObstetric/fetal doppler ultrasound
Secondary	

To evaluate RLYB212 exposure in the neonate at delivery	
Concentration of RLYB212 in cord blood

To assess the safety of RLYB212 in the HPA-1a positive neonate	
Type, seriousness, and incidence of AEs including fetal/neonatal AEsPhysical examination findings, including APGAR scoresVital signs

To assess the immunogenicity of RLYB212	
Development of ADAs

To assess pregnancy and neonatal outcomes following antenatal RLYB212 administration	
Number of spontaneous abortionsNumber of elective abortionsNumber of stillbirthsNumber of premature birthsNumber of full term births (≥ 37 completed weeks of gestation)Overall health and development of infants at 4-6 weeks and 12 months of age

To assess the occurrence of neonatal thrombocytopenia following antenatal RLYB212 administration	
Neonatal thrombocytopenia^a and severe neonatal thrombocytopenia

To assess the occurrence of HPA-1a alloimmunization	
Presence of maternal anti-HPA-1a alloantibodies at Week 10 post pregnancy^b

ADA = anti-drug antibody; AE = adverse event; APGAR = Appearance, Pulse, Grimace, Activity, and Respiration; ECG = electrocardiogram; HPA-1a = human platelet antigen 1a; PK = pharmacokinetic(s); SC = subcutaneous.

^a Evaluation of neonatal thrombocytopenia will be based on the umbilical cord sample taken at parturition.

^b For pregnancies that do not result in a live birth, the assessment of alloimmunization will be at 10 weeks from the date of the pregnancy-terminating event (ie, abortion [spontaneous/elective] or stillbirth).

A non-interventional (observational) sub-study (IPA2202A) is planned based on the phased approach to participant enrollment that results from the sequential cohort design. Because of the rarity of the potential occurrence of HPA-1a alloimmunization, the non-interventional (observational) sub-study will serve to augment an ongoing FNAIT Natural History Study (NCT05345561), ie, generating natural history data on the occurrence of HPA-1a alloimmunization and pregnancy/neonatal outcomes in women at higher FNAIT risk. Descriptions of the non-interventional (observational) sub-study design are presented separately across this protocol.

Objectives and Endpoints (Non-interventional [Observational]/Study IPA2202A)

Objective	Endpoint

To inform the frequency of HPA-1a alloimmunization among pregnant women identified at higher FNAIT risk	
Occurrence of anti-HPA-1a maternal alloimmunization at Week 10 postpartum^a

To inform the frequency of pregnancy outcomes among pregnant women identified at higher FNAIT risk	
Rate of spontaneous abortion, defined as non-deliberate fetal death which occurs prior to 19 weeks of gestationRate of elective abortion, defined as deliberate termination of pregnancy at any time in gestationRate of stillbirth, defined as non-deliberate fetal death anytime in gestation on or after 19 weeks of gestationRate of premature birth, defined as live birth prior to 37 completed weeks of gestationRate of full term birth (≥ 37 completed weeks of gestation)

To inform the frequency, where data are available, of neonatal thrombocytopenia in infants born to women who have alloimmunized, as determined by detectable anti-HPA-1a antibody at Week 10 postpartum^a	
Neonatal thrombocytopenia and severe neonatal thrombocytopenia, as determined by a platelet count $< 150 \times 10^9/L$ and $< 50 \times 10^9/L$, respectively, where data are available

^a For pregnancies that do not result in a live birth, the assessment of alloimmunization will be at 10 weeks from the date of the pregnancy-terminating event (ie, abortion [spontaneous/elective] or stillbirth).

[figure not shown]
Overall Design

This study is a single-arm, open-label, multicenter study of RLYB212 in HPA-1b/b pregnant participants at higher risk for the occurrence of HPA-1a alloimmunization and FNAIT. A laboratory testing paradigm will be applied at screening to identify women at higher risk for HPA-1a alloimmunization. Study IPA2202 is comprised of three phases: a two-part screening phase, an antenatal treatment phase, and a postpartum follow-up phase (Figure 1-1). Study duration for each participant is anticipated to be ~44 weeks, inclusive of the screening visits through the Week 10 postpartum visit. For each child born during the study, the duration is anticipated to be ~12 months.

For the non-interventional (observational) sub-study (IPA2202A), the same two-part screening phase for the intervention, as applicable, is followed by a postpartum/safety follow-up phase. The sub-study duration is anticipated to be ~44 weeks, inclusive of the screening visits through the Week 10 postpartum visit.

The overall design of the Phase 2 study, including the non-interventional (observational) sub-study, is presented in Figure 1-1.

Figure 1-1 Overall Study Design (Interventional and Non-interventional [Observational])

FNAIT = fetal and neonatal alloimmune thrombocytopenia; ICF = informed consent form; PK = pharmacokinetic; SC = subcutaneous.

For Screening (Part 2)/ICF: Enrollment planned for 8 eligible participants for whom the pregnancy results in a live birth and who are evaluable for PK and safety assessments.

Screening Phase

In participants presenting at GW 6 or after who provide informed consent, blood samples will be collected at the Screening Part 1 visit to assess for higher risk for the occurrence of HPA-1a alloimmunization during their pregnancy. The first test will be a test for maternal HPA-1 genotype. In participants identified as HPA-1b/b (ie, HPA-1a negative), subsequent tests will be performed to confirm the participant has an HLA-DRB3*01:01 positive genotype, is anti-HPA-1a alloantibody negative, and is carrying an HPA-1a/b (ie, HPA-1a positive) fetus.

Participants who meet all eligibility criteria in Screening Part 1 (ie, HPA-1b/b and HLA-DRB3*01:01 positive genotype; anti-HPA-1a alloantibody negative; fetal HPA-1a/b genotype) and who provide informed consent for Screening Part 2 (Visit 1/schedule of activities [SoA], [Table 1-3](#)) will be assessed to determine if they meet all eligibility criteria to enter the antenatal treatment phase of the study and to receive RLYB212 in accordance with protocol dose regimen.

Antenatal Treatment Phase

For participants who meet all the eligibility criteria at Screening Part 2 (Visit 2/[Table 1-3](#)), dosing with RLYB212 will be initiated at Visit 3, which must occur no later than GW 16. If the fetal HPA-1 genotype is pending and will not be available by the planned visit at ~GW 16, the subject will be dosed with the initial dose of RLYB212 pending the result (of the replicate tests), provided all other Screening Part 2 criteria are met. A second dose of RLYB212 will not be given if definitive fetal HPA-1a results are not available by Visit 4 (~GW 20). If the fetal HPA-1a genotype data are only available after the initial dose of RLYB212 is given and the fetus is HPA-1b/b, ie, not at risk for HPA-1a alloimmunization, the participant will be discharged from the study to receive normal prenatal care and follow-up by their physician. In this case, the participant would have been determined not to be at risk for development of HPA-1a alloimmunization and FNAIT.

Dosing will be continued at the protocol-specified dose regimen during the pregnancy with the final dose of RLYB212 administered within 24 hours (\pm 24 hours) of parturition.

Postpartum/Safety Follow-up

Upon completion of the antenatal treatment phase, participants will be monitored through 10 weeks postpartum. Safety follow-up for the neonate/infant will be at 4-6 weeks and 12 months following parturition. For pregnancies that do not result in a live birth, monitoring will be for 10 weeks from the date of the pregnancy terminating event.

Statistical Considerations

No statistical hypothesis testing will be performed in this study. No formal interim analyses will be conducted. Preliminary data may be used for summary purposes and for communication with health authorities.

Number of Participants

It is anticipated that approximately 5,000 participants will be screened to enroll 8 eligible participants for whom the pregnancy results in a live birth and who are evaluable for PK and safety assessments. Up to 4 participants may be replaced if they were assigned to study drug but did not receive the study drug. Participants may be replaced for reasons other than clinical safety, including insufficient PK sample collection to characterize pharmacokinetics.

Eligibility Criteria

Eligibility for this study will be established using a two-part screening procedure. Screening Part 1 will identify those participants who are at higher risk for the occurrence of maternal HPA-1a alloimmunization and FNAIT in their pregnancy. Women in their first or subsequent pregnancy may be included in the study. If a participant meets eligibility criteria in Screening Part 1, they may proceed to Screening Part 2 to determine their eligibility for enrollment and subsequent treatment with RLYB212. If a participant is eligible at Screening Part 2 for the antenatal treatment phase, but the cohort has been fully enrolled, the participant will be requested to consent for enrollment in the non-interventional (observational) sub-study ([Table 1-1](#)).

Inclusion Criteria to be Confirmed at Screening Part 1

1. Written/signed informed consent (for Screening Part 1)
2. 18-45 years of age
3. Pregnant women who present at GW 6 or after and confirmed to be:
 - a. HPA-1b/b (HPA-1a negative)
 - b. HLA-DRB3*01:01 positive
 - c. Anti-HPA-1a alloantibody negative
 - d. Carrying an HPA-1a/b (HPA-1a positive) fetus

Exclusion Criteria to be Confirmed at Screening Part 1

1. Prior history of HPA-1a-related FNAIT
2. Prior history of HPA-1a alloimmunization
3. Prior history of platelet transfusion or other blood transfusions
4. Body mass index (BMI) $\geq 35 \text{ kg/m}^2$

Eligibility Criteria for Study Intervention

Participants who meet all eligibility criteria in Screening Part 1 (ie, HPA-1b/b and HLA-DRB3*01:01 positive genotype; anti-HPA-1a alloantibody negative; fetal HPA-1a/b

genotype) and who provide informed consent for Screening Part 2, will be assessed for eligibility to enter the study's antenatal treatment phase and to receive treatment with RLYB212 provided all inclusion and no exclusion criteria are met.

Inclusion Criteria for Study Drug Administration to be Confirmed at Screening Part 2

1. Written/signed informed consent (for Screening Part 2)
2. 18-45 years of age
3. Pregnancy no later than GW 16 at the time of first study drug administration as determined by the principal investigator or qualified staff

Exclusion Criteria for Study Drug Administration to be Confirmed at Screening Part 2

Participants are excluded from the study if any of the following criteria apply:

1. Multiple pregnancy (> 1 fetus)
2. Known sensitivity and/or immediate hypersensitivity to any components of RLYB212 or its formulation
3. History of hypersensitivity to protein therapeutics
4. Any participant with a history of past or current intravenous immunoglobulin (IVIG) use for an underlying disease (eg, autoimmune disease)
5. Requires ongoing systemic corticosteroid or systemic immunosuppressive treatment for any reason
6. History of pre-eclampsia in a previous pregnancy
7. Participants with an in vitro fertilized pregnancy or serving as pregnancy surrogates
8. Current (or within the last 90 days) participation in another clinical study and have received an investigational drug and device within the last 90 days
9. Participants known or suspected of not being able to comply with this study protocol
10. History of any connective tissue or autoimmune or autoinflammatory disease, especially autoimmune thrombocytopenia
11. Any co-morbid medical or obstetric condition(s), laboratory abnormality, concomitant treatment, or other reason that, in the investigator's opinion, could adversely affect the safety of the participant and/or fetus, impair the assessment of study results, or preclude compliance with the study.

Non-interventional (Observational) Sub-study (IPA2202A) Eligibility and Population

It is anticipated that a limited number of participants will be enrolled in the non-interventional (observational) sub-study. Criteria for enrollment in the sub-study, with reference to the two-part Screening phase, include the following:

Table 1-1 Anticipated Eligibility Criteria for Sub-study

Screening Part 1	Screening Part 2
In the Antenatal Treatment Phase, the enrollment for the current sentinel or sequenced cohort has been fulfilled	
Results of Screening are only available after the first study drug administration window (by GW 16) has passed	
Refusal of consent to Screen Part 2	Screen Failure
---	Withdrawal of consent for Antenatal Treatment Phase

Intervention Groups and Duration

All interventional participants will receive SC RLYB212 administered using a vial and syringe.

RLYB212 treatment will be initiated at the dosing visit (Visit 3) with an initial SC dose of 0.12 mg no later than GW 16, followed by SC doses of 0.06 mg Q4W and with a final 0.06 mg dose administered within 24 hours (\pm 24 hours) of parturition.

A key goal of the study is to define the RLYB212 dose regimen that achieves the pre-determined target exposure range through parturition. Modification of the RLYB212 dose regimen may therefore be necessary, to ensure desired steady state concentrations are maintained through pregnancy and parturition between a target lower bound of \sim 3 ng/mL and a target upper bound of \sim 10 ng/mL.

Modification of RLYB212 dose/dose frequency may be made within a cohort or between cohorts, based on available PK data from participant(s) with a completed pregnancy. Dose modifications are not anticipated during the pregnancy of an individual participant.

Data Monitoring Committee

[figure not shown]
An independent data monitoring committee (DMC) will monitor safety outcomes and study conduct and will provide recommendations for consideration by the Sponsor regarding the continuation of the study, dosing of further participants in the study, or stopping the study for all participants or subgroups of participants in the study. Safety data will include, but not be limited to, those outcomes listed as primary and secondary endpoints.

The Sponsor will propose a detailed mandate to the DMC and review this with the DMC prior to the initiation of screening. A detailed DMC charter and operating rules will be prepared and signed by DMC members before study start.

[figure not shown]

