Study IPA2001 assessed the safety and PK of SC administered RLYB212 following single dose administration (0.21 mg) and multiple dose administration (0.29 mg on Day 1 followed by 0.1 mg every 2 weeks for an additional 10 weeks). RLYB212 was well tolerated in both cohorts of the study. The majority of treatment emergent adverse events (TEAEs) were reported as mild and no severe TEAEs, serious adverse events (SAEs) or TEAEs leading to withdrawal from study treatment were reported. Six possibly related TEAEs were reported in 3 participants (18.8%), all of whom received RLYB212 in the multiple dose cohort. The most common of the possibly related TEAEs was headache (2 events in 2 participants) and two of the possibly related TEAEs were of moderate severity (headache and muscle spasms). There were no clinically meaningful findings related to clinical laboratory evaluations. There were no clinically meaningful findings related to vital signs, electrocardiograms (ECGs), or physical examinations. RLYB212 displayed a PK profile consistent with an SC-administered monoclonal antibody, with a median t_{max} that ranged from 7 to 14 days, followed by a mono-exponential decline with a mean serum half-life of ~ 25 days. Two RLYB212 participants showed positive results for ADAs against RLYB212 (1 transient in Cohort 1 and 1 persistent with low titer in Cohort 2). No clinical findings attributable to ADAs were observed in these 2 participants and based on the similarity in PK profiles between participants with ADA positive and ADA negative results, the development of anti-RLYB212 antibodies had no clinically significant effect on the PK of RLYB212.

In Study IPA2003, a Phase 1b PoM/PoC study, the ability of RLYB212 to rapidly eliminate HPA-1a positive platelets in HPA-1b/b participants was confirmed. In this study, participants received a single SC dose of RLYB212 (0.09 or 0.29 mg) or placebo on Day 1, followed by a transfusion of HPA-1a positive platelets on Day 8. Assessments of HPA-1a positive platelet elimination were performed through Day 15 and the post treatment safety follow-up period

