	
Cell-free fetal DNA collected for fetal genotyping is at low levels before GW 10 (<3% of total maternal circulating cfDNA and gradually increases by about 1% by Week 20). [15] Due to these low levels of fetal DNA prior to GW 16, confirmation of fetal HPA-1 genotype may come after initial dose of RLYB212 at GW 16. (Section 8.1.1 and Section 8.1.2). Consequently, some participants carrying a potentially HPA-1b/b fetus will be exposed to the loading dose of RLYB212 despite not being at risk for alloimmunization.	
The Phase 2 study (IPA2202) employs sentinel subject dosing through pregnancy followed by two sequential, sequenced cohorts. Modification of the RLYB212 dose regimen may be performed during the study based on available PK data from participant(s) with a completed pregnancy, to ensure desired steady state concentrations are maintained through pregnancy and parturition between a target lower bound of ~3 ng/mL and a target upper bound of ~10 ng/mL.For women receiving RLYB212 loading dose (0.12 mg) before the fetal genotype is definitively determined, there is a ~85% chance that the fetus will be HPA-1a/b and hence express the antigen (due to the prevalence of the HPA-1b gene and application of the Hardy-Weinberg principle in the case of unknown paternal genotype). In that case, all aspects to mitigate fetal/placental harm noted above will be in place and the loading dose will have been administered appropriately. There remains a roughly 15% chance, however, that the fetus will be determined to be HPA-1b/b, consistent with the maternal genotype. In this case, RLYB212 administration will be stopped, and the pregnancy will be followed for an additional 4 weeks for safety and PK assessment. Since RLYB212 is directed against the HPA-1a epitope, which neither mother nor fetus express, the antibody will not bind to maternal or fetal tissues. Therefore, RLYB212 is expected to pose no risk other than that of any exogenous monoclonal antibody, as outlined under “Maternal Risks” within this table.Fetal doppler ultrasound monitoring will be performed at regular intervals during the study and consistent with obstetric standard of care, to detect any evidence of placental structural abnormality, organ pathology, hemorrhage, or delayed growth in the fetus.A cord blood sample will be collected at delivery to evaluate fetal exposure to RLYB212.

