7 DISCONTINUATION OF STUDY INTERVENTION AND PARTICIPANT DISCONTINUATION/WITHDRAWAL

7.1 Discontinuation of Study Intervention

In rare instances, it may be necessary for a participant to permanently discontinue (definitive discontinuation) study intervention. If study intervention is definitively discontinued, the participant will remain in the study to be evaluated for pregnancy outcomes and postnatal follow-up in the event of live birth, and for anti-HPA-1a antibody determination. If treatment is discontinued because a delayed cell-free fetal DNA determination reveals the fetus is HPA-1b/b, the subject will also return 4 weeks after RLYB212 dosing for a safety visit, the context of which will be the same as Visit 5 in the SoA ([Section 1.3](#)). Participants withdrawing consent to be in the study or administrative reasons for discontinuation should proceed directly to the end of study (EOS) visit (Week 10 postpartum), if possible.

Refer to the SoA ([Section 1.3](#)) for details of the data to be collected at the time of discontinuation of RLYB212, follow-up, and for any further evaluations that need to be completed. Permanent discontinuation of RLYB212 for safety-related reasons will not be followed by a rechallenge.

Information on the study assessments and procedures is provided in [Section 8](#).

7.1.1 *Temporary Discontinuation*

In the event of temporary discontinuation of study intervention, the investigator should contact the medical monitor/Sponsor immediately. Further course of action will be decided upon by discussion between investigator, Sponsor, and with the DMC, as needed.

7.1.2 *Study Stopping Rules*

In the event of maternal death¹, treatment will be withheld for all study participants, pending Sponsor evaluation and DMC recommendation.

Following occurrence of a maternal/fetal/neonatal common terminology criteria for adverse events (CTCAE) Grade 4¹ or Grade 5 event as specifically described by Spencer et al [17] or any of the fetal/neonatal AEs specified in [Section 10.3.3 \(Appendix 1\)](#), treatment with RLYB212 will not be initiated in any new study participants pending Sponsor evaluation and DMC recommendation. Reference is made to [Section 10.3.3 \(Appendix 1\)](#) for guidance on using the maternal and fetal AE severity grading criteria.

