7.2 Participant Discontinuation/Withdrawal from the Study

A participant may withdraw from the study at any time at their own request or may be withdrawn at any time at the discretion of the investigator for safety, behavioral, compliance, or administrative reasons.

Participants for whom treatment is withdrawn but who retain consent to continue in the study should be followed through all activities in the study SoA ([Section 1.3](#)). Those who withdraw consent should have EOS (Week 10 postpartum) procedures performed as their end of study visit.

If the participant withdraws consent for disclosure of future information, the Sponsor may retain and continue to use any data collected before such a withdrawal of consent.

Any participants discontinuing the study early for reasons unrelated to pregnancy outcomes or safety will be replaced.

Up to 4 participants may be replaced if they were assigned to study drug but did not receive the study drug. Participants may also be replaced for reasons other than clinical safety, including but not limited to insufficient PK sample collection to evaluate the PK profile of RLYB212 during pregnancy.

In addition, where the outcome of the pregnancy is not a live birth, these participants may be replaced. Any decision regarding the replacement of participants will be discussed with the DMC prior to additional enrollment of participants into the study.

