Screening Part 1 is an initial visit that includes the informed consent, demographic questioning (including obstetric history), and the collection of a blood sample for FNAIT testing (Table 1-2). This visit is to take place no earlier than GW 6. Individuals will consent to HPA-1 genotyping (Test 1) and, if HPA-1b/b, subsequent screening for HLA-DRB3*01:01 (Test 2), anti-HPA-1a antibodies (Test 3), and confirmation of fetal HPA-1a genotype (Test 4), as required.

Two distinct samples and analyses are performed, per industry practice, to confirm absence of the HPA-1b allele in the fetus, with timing between sampling ~2 weeks.

8.1.2 Screening Part 2

Participants who meet all eligibility criteria in Screening Part 1 (SoA, Table 1-3, ie, HPA-1b/b and HLA-DRB3*01:01 positive genotype; anti-HPA-1a alloantibody negative; fetal HPA-1a/b genotype) and who provide informed consent for Screening Part 2 (SoA, Table 1-3) will be assessed to determine if they meet all eligibility criteria to enter the antenatal treatment phase and to receive treatment with RLYB212 according to the protocol.

Dosing with RLYB212 will be initiated at Visit 3, which must occur no later than GW 16. That is, if the fetal HPA-1 genotype is pending and will not be available by the planned baseline visit at GW 16, the subject will be dosed with the initial dose of RLYB212 pending the result (of the

replicate tests), provided all other Screening Part 2 criteria are met. A second dose of RLYB212 will not be given if definitive fetal HPA-1a results are not available by Visit 4 (~GW 20). If the fetal HPA-1a genotype data become available after the initial dose of RLYB212 is given and the fetus is HPA-1b/b, ie, not at risk for HPA-1a alloimmunization, the participant will be discontinued from treatment, followed at a safety visit 4 weeks later and then discharged from the study to receive normal prenatal care and follow-up by their physician. In this case, the participant would have been determined not to be at risk for development of HPA-1a alloimmunization and FNAIT.

The study has been designed with multiple sequential cohorts ([Section 1.2.1](#)). Therefore, if a participant has been determined to be eligible for RLYB212, but the cohort has been fully enrolled, the participant will be requested to consent for the non-interventional (observational) sub-study.

Eligibility for the non-interventional (observational) sub-study is presented in [Table 1-1](#).

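### The protocol gives conflicting follow-up rules for a woman dosed while the fetal genotype is pending whose fetus proves HPA-1b/b, and its dose-2 deadline names the wrong visit

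*Protocol*

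**What the plan says.** The case is a woman given the 0.12 mg loading dose by GW 16 with the fetal result outstanding, whose fetus is later typed HPA-1b/b. Five places in the Protocol bear on what happens next.

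- **Synopsis, Antenatal Treatment Phase:** "the participant will be discharged from the study to receive normal prenatal care and follow-up by their physician". No further study visit is mentioned.
- **Section 8.1.2:** she is "followed at a safety visit 4 weeks later and then discharged from the study".
- **Section 2.3.1, Table 2-1:** dosing stops and "the pregnancy will be followed for an additional 4 weeks for safety and PK assessment".
- **Section 7.1:** after definitive discontinuation "the participant will remain in the study to be evaluated for pregnancy outcomes and postnatal follow-up in the event of live birth", and for anti-HPA-1a testing. It then names the HPA-1b/b case and says "the subject will also return 4 weeks after RLYB212 dosing for a safety visit", adding "the context of which will be the same as Visit 5 in the SoA".
- **Section 7.2:** "Participants for whom treatment is withdrawn but who retain consent to continue in the study should be followed through all activities" in the schedule.

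On the second dose, the Synopsis and Section 8.1.2 both withhold it unless a definitive fetal result is in hand by a visit that they call Visit 4 and date at ~GW 20.

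**The concern.** A site with such a woman has two incompatible instructions: discharge her at or before about 4 weeks, or follow her to delivery and beyond. Even the 4-week visit has no agreed start. Section 7.1 counts from dosing, while Section 8.1.2 and Table 2-1 can be read as counting from discontinuation.

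If the shorter rule is followed, the outcome of a pregnancy exposed to RLYB212 is lost, although pregnancy and neonatal outcomes after antenatal dosing are a secondary objective. Under Section 8.5.1, an SAE after discharge reaches the sponsor only if the investigator happens to learn of it and considers it reasonably related. No section ties the 4-week limit to drug clearance.

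The dose-2 deadline is a working dosing rule. Read by its visit number, it could withhold Dose 2 from an eligible woman whose result arrives between GW 18 and GW 20.

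**Working it through.** **1. Do the follow-up rules conflict?**

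| Place | 4-week visit | After that |
|---|---|---|
| Synopsis | not mentioned | discharged |
| 8.1.2 | yes | discharged |
| Table 2-1 | followed 4 more weeks | nothing stated |
| 7.1 | yes, in addition | pregnancy outcome, postnatal follow-up, antibody test |
| 7.2 | per schedule | all scheduled activities |

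Section 7.1 cannot be set aside as a general rule that yields to a specific one. It names the HPA-1b/b case itself, and its word *also* adds the 4-week visit to continued follow-up. It says postnatal rather than infant follow-up, but the postnatal schedule in Table 1-3 includes infant status at 4-6 weeks and 12 months, so that is the natural reading.

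**2. Follow-up time lost under the shorter rules**

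Inputs: dosing at GW 16 (the latest allowed), birth at GW 40 (Table 1-3, footnote b), stillbirth counted from GW 19 (Section 9.4.3).

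- Post-dose weeks: 40 − 16 = 24. Stillbirth window: 40 − 19 = 21 weeks.
- 4 weeks from dosing, last visit GW 20: 40 − 20 = 20 weeks unobserved; 20/24 = 83% of post-dose time, 20/21 = 95% of the stillbirth window.
- 4 weeks from discontinuation at GW 20, last visit GW 24: 40 − 24 = 16 weeks; 16/24 = 67% and 16/21 = 76%.
- Synopsis read literally, result and discharge at GW 16-20: 20 to 24 of 24 weeks, 83-100%.

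Birth at term and the infant outcomes are missed in every case. These are shares of calendar time, not of risk.

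**3. Drug still present when follow-up ends**

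Section 2.2.2.2 reports, in non-pregnant HPA-1b/b volunteers, a median time to peak "that ranged from 7 to 14 days, followed by a mono-exponential decline with a mean serum half-life of ~ 25 days". Fraction of peak at day d = 2^(−(d − tmax)/t½), with tmax = 7 or 14 days.

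| Day | t½ = 25 d (protocol) | t½ = 15 d (assumed, for pregnancy) |
|---|---|---|
| 28 | 2^(−21/25) = 0.559; 2^(−14/25) = 0.678 | 0.379; 0.524 |
| 56 | 2^(−49/25) = 0.257; 2^(−42/25) = 0.312 | 0.104; 0.144 |
| 168 (GW 40) | 0.012; 0.014 | not computed |

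So 56-68% of peak remains at 4 weeks and 26-31% at 8 weeks, or 38-52% and 10-14% with the shorter assumed half-life. About 1% remains at term, so what is lost is outcome data, not a useful cord-blood drug level.

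**4. How often it would arise**

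Table 2-1 gives roughly a 15% chance of an HPA-1b/b fetus for each woman dosed while pending. The number dosed while pending, n, is not stated. P(at least one) = 1 − 0.85^n: 15% for n = 1, 39% for n = 3, 73% for n = 8. The expected count at n = 8 is 8 × 0.15 = 1.2.

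**5. The dose-2 deadline**

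Gestational week = 16 + weeks since the initial dose (Table 1-3).

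- Visit 4: Week 2, 16 + 2 = ~GW 18, PK sample and no dose.
- Visit 5: Week 4, 16 + 4 = ~GW 20, Dose 2.

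The printed pairing of Visit 4 with ~GW 20 does not reproduce. SAP Table 4 agrees with the schedule: Visit 4 is Week 2, and the second dose is at Visit 5, Week 4. Section 7.1 also equates 4 weeks after dosing with Visit 5. The deadline is off by one visit, or 2 weeks.

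**The case against.** The best reply is that three places address this exact case and none continues beyond about 4 weeks, so a site would follow them. Table 2-1 gives a reason for low risk: neither mother nor fetus carries the target antigen. Such a woman is outside the target population, and the neonatal safety objective is limited to HPA-1a positive neonates. Section 7.2 applies to women who keep consent to continue, which may not fit someone the protocol itself discharges. The visit number is a slip that the printed ~GW 20 largely corrects. The study stopped with one participant enrolled and will report listings only (SAP Section 4.9).

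Much of this limits the consequence. Expected risk is low, so the issue is missing data rather than foreseen harm. The case is uncommon, and effects on the final results are probably slight. Section 7.2 is supporting text rather than decisive. Neither reading of the deadline permits a second dose without a confirmed genotype.

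The conflict remains, because Section 7.1 names the same case. The pregnancy-outcome objective is not restricted by fetal genotype, and any dosed woman belongs to the Safety Analysis Set. Table 2-1 itself lists exposure of an HPA-1b/b fetus among the fetal risks, which argues for collecting the outcome.

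**Conclusion.** Both parts hold. Sections 7.1 and 7.2 require follow-up that the Synopsis, Section 8.1.2 and Table 2-1 cut off. Under the 4-week rules, 67-83% of post-dose pregnancy time is unobserved, and birth at term and infant outcomes are not collected. This assumes dosing at GW 16, birth at GW 40 and, for the lower figure, discontinuation at GW 20. The dose-2 deadline is mislabelled by one visit.

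This should be fixed, as a defect in the protocol as written. The documents do not say whether the one enrolled participant was dosed while the genotype was pending, so no effect on the reported data can be shown.

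**What to change.** - **Follow-up.** Amend the Synopsis, Table 2-1 and Section 8.1.2 to match Sections 7.1 and 7.2: a visit 4 weeks after dosing with Visit 5 content (safety and PK), then follow-up to pregnancy outcome and of the infant. Cutting Section 7.1 back instead would remove its conflict with Section 8.1.2, but it would leave exposed pregnancies without an outcome and at odds with Section 7.2.
- **Dose 2.** Change the deadline in the Synopsis and Section 8.1.2 to Visit 5 (~GW 20).
- **Clerical.** The replicate fetal test should confirm absence of the HPA-1a allele, not HPA-1b (Protocol Table 1-2 and Section 8.1.1; SAP Table 2). An HPA-1b/b mother always transmits HPA-1b, and Protocol Table 8-1 is already right.
- **SAP Section 4.9.** State that the listings cover every dosed woman and her infant, whatever the fetal genotype. The FAS and NFAS definitions would exclude this woman and her infant, since she fails the fetal-genotype criterion, though this matters little now that only listings are planned.

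The cost is wording in three follow-up passages and two deadline sentences, plus the small corrections above. For each such woman it confirms the birth assessments, the Week 10 postpartum visit with antibody test, and infant visits at 4-6 weeks and 12 months with developmental screening. That is a real burden for someone no longer at risk of alloimmunization, but Sections 7.1 and 7.2 already ask for it.
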